Period 3, Post-Administration Collection (PAC): The RSS and RMS for efficacy evaluation will be collected during Period 3. There will be 3 PAC periods: PAC1 (Weeks 18-20), PAC2 (Weeks 37-39) and PAC3 (Weeks 50-52). The primary efficacy evaluation period will be PAC3, commencing 50 weeks after randomisation and outside of any and all relevant seasonal allergy periods for the subject. The use of allergy rescue medication during the PAC periods will be according to a pre-specified Rescue Medication Plan (see Appendix 3). Data collected in the periods commencing at 18 weeks (PAC1) and 37 weeks (PAC2) after randomisation will be used for exploratory efficacy analyses.

At the Period 3 Follow-Up Visit 5, 52 weeks from first dosing, subjects will undergo a final safety assessment.

The duration of the study for each subject will be approximately 62 weeks.

VERSION FINAL 4.0 CONFIDENTIAL

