### 3.2.2 Secondary Efficacy Variables

The secondary efficacy variables are

- Clinical Global Impression of Change in Rhinoconjunctivitis Symptoms for the HDM-SPIRE treatment groups compared with placebo at the end of study.
- Mean TRSS in the HDM-SPIRE treatment groups compared with placebo during the

VERSION FINAL 4.0 CONFIDENTIAL PAGE 23 OF 92

- PAC3 period.
- Mean component scores of the TRSS (nasal and non-nasal) in the HDM-SPIRE treatment groups compared with placebo during the PAC3 period.
- Mean RMS in the HDM-SPIRE treatment groups compared with placebo during the PAC3 period.
- Mean Rhinoconjunctivitis Quality of Life Questionnaire (RQLQ) score in the HDM-SPIRE treatment groups compared with placebo at the end of the PAC3 period.
- Number of days subjects in the HDM-SPIRE treatment groups have no moderate or severe RSS symptoms without rescue medication usage compared with placebo during the PAC3 period.

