#### The PAC periods are:

- PAC1: Weeks 18-20 (±2 days) Visits 4A and 4B will occur on the first and last day, respectively. Visit 4B will take place at the same time as the Dosing Visit 3F. PAC1 may occur during a pollen period to which the subject has clinically significant symptoms.
- PAC2: Weeks 37-39 (±2 days), Visits 4C and 4D will occur on the first and last day, respectively. PAC2 may occur during a pollen period to which the subject has clinically significant symptoms.
- PAC3: Weeks 50-52 (±2 days), Visits 4E and 4F will occur on the first and last day, respectively. The PAC3 period must start after the end of the pollen period for all relevant seasonal allergens to which the subject has clinically significant symptoms

VERSION FINAL4.0 CONFIDENTIAL PAGE 52 OF 92

and must complete at least 1 week before the anticipated start date of the Spring pollen season for any allergen to which the subject has clinically significant symptoms.

If a subject requires medication for allergy symptoms during a PAC period they may take allergy rescue medications from the Rescue Medication Package provided in accordance with the Rescue Medication Plan (Appendix 3).

At the start of each PAC (Visits 4A, 4C and 4E), the following assessments will be performed:

- Vital Signs (sitting or semi-recumbent)
- Recording of AEs.
- Recording any changes in concomitant medications since last visit.
- The subject must be retrained on how to follow the Rescue Medication Plan (Appendix 3).
- Allergy rescue medication will be dispensed.
- Subjects will be reminded to check with the Investigator before they start any new medications other than their allergy rescue medication.
- A new pDiary will be issued.
- At the end of the visit, subject will be provided with their eDiary to record the following information on a daily basis, first thing in the morning, for the next 3 weeks:
  - o RSS using a 4 point categorical scale
  - o ASS
  - o Allergy rescue medication use

In addition, at the start of each PAC period, subjects will record their RSS using a VAS. This assessment will be based on the subject's assessments of their symptoms over the preceding week. Subjects will be asked to rate their allergy symptoms on a visual scale where 0 = no allergy symptom and 10 = my allergy symptom is the worst it could possibly be. This assessment will be recorded on the eDiary.

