#### 7.5.3.2.4 Proportion of Symptom-Free Days

The difference in proportion of Symptom-Free Days between HDM-SPIRE treatment groups compared with the placebo group will be calculated and treatment comparisons made using the same model as specified for the primary efficacy analysis.

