#### 7.5.3.3 Exploratory Analysis

The PAC1 and PAC2 periods will be analysed by the same methods as for the PAC3 period. These analyses will be considered exploratory, since they may be confounded by seasonal allergies. Where appropriate, the same covariates will be included in the exploratory analysis statistical models as for the primary efficacy analysis.

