##### Analysis of Mean Total Rhinoconjunctivitis Symptom Score

A point estimate and two-sided 95% confidence interval for the difference in adjusted means between the active treatment groups and placebo is to be calculated using the same MMRM as described in Section 15.1.3 Primary Analysis of Primary Efficacy Variable.

- The treatment difference corresponding to the PAC3 period is to be utilised for the secondary analysis
- The treatment difference corresponding to the PAC1 and PAC2 periods are to be utilised as exploratory analyses

Observed and change from Baseline values are to be summarised by descriptive statistics for the PAC1, PAC2 and PAC3 periods by treatment group.

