##### Analysis of Proportion of Well Days

A point estimate and two-sided 95% confidence interval for the difference in adjusted means between the active treatment groups and placebo is to be calculated using the same MMRM as described in Section 15.1.3 Primary Analysis of Primary Efficacy Variable.

The treatment difference corresponding to the mean proportion of symptom free days of the PAC1, PAC2 and PAC3 periods is to be utilised for the secondary analysis.

Observed and change from Baseline values are to be summarised by descriptive statistics for the PAC1, PAC2 and PAC3 periods by treatment group.

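### SAP 15.2.1.5 makes PAC1, PAC2 and PAC3 together the secondary analysis of well days, whereas the protocol's endpoint is PAC3 alone

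*SAP*

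**What the plan says.** **Protocol.** Section 3.2.2 lists as a secondary variable the number of days on which subjects have "no moderate or severe RSS symptoms without rescue medication usage compared with placebo during the PAC3 period". Section 7.5.3.2.4, which calls the variable a proportion of symptom-free days, names no period but has "treatment comparisons made using the same model as specified for the primary efficacy analysis"; in 7.5.3.1.1 the treatment contrast of that model is at PAC3. On the two earlier periods, section 3.1 says that their data "will be used for exploratory efficacy analyses", and section 7.5.3.3 gives the reason: "These analyses will be considered exploratory, since they may be confounded by seasonal allergies". Section 6.2.3.1 adds that "PAC1 may occur during a pollen period to which the subject has clinically significant symptoms" and says the same of PAC2, while PAC3 has to lie outside the relevant pollen seasons.

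**SAP.** Section 15.2.1.5 derives a proportion of well days separately for the baseline period and each PAC period, and refers to the primary MMRM for the analysis. It then says that the treatment difference for the "mean proportion of symptom free days of the PAC1, PAC2 and PAC3 periods is to be utilised for the secondary analysis". In the section on mean TRSS (15.2.1.1) the corresponding sentence is "The treatment difference corresponding to the PAC3 period is to be utilised for the secondary analysis", followed by a bullet that makes the PAC1 and PAC2 differences exploratory.

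**The concern.** The two documents name different periods for the same secondary endpoint. The protocol chose PAC3 on purpose: it is the one post-treatment period scheduled away from pollen that affects the subject. PAC1 and PAC2 may contain symptoms caused by pollen, and a mite-specific product has no evident reason to change those. PAC1 also falls while injections are still being given, so the arms are not at comparable points of their courses.

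If the study report follows the SAP, it may present as a protocol secondary endpoint a quantity that the protocol did not define, or give two exploratory comparisons secondary standing. Because the sentence can be read in two ways, the choice between them could also be made after the data are unblinded.

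**Working it through.** **1. Comparison across the SAP's period-modelled secondary endpoints.**

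| Endpoint (SAP section) | Secondary result | PAC1 and PAC2 |
|---|---|---|
| TRSS (15.2.1.1) | PAC3 | exploratory |
| Nasal and non-nasal components (15.2.1.2) | PAC3 | exploratory |
| RMS (15.2.1.3) | PAC3 | exploratory |
| **Well days (15.2.1.5)** | **PAC1, PAC2 and PAC3** | **part of the secondary analysis** |
| RQLQ (15.2.1.6) | PAC3 | exploratory |
| Asthma symptom score (15.2.1.7) | PAC3 | exploratory |

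Well days is the only exception. Neither its section nor the SAP modification history explains the departure. Well days at PAC1 and PAC2 are not among the protocol's listed exploratory endpoints (3.2.3) either. The sentence also speaks of symptom-free days in a section that defines well days, which suggests an editing slip.

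**2. Position of PAC1 in the dosing schedule.** Protocol Table 2 gives doses at weeks 0, 4, 8, 12, 16, 20, 24 and 28. When PAC1 opens at week 18, the 8 x 12 nmol arm has had 5 of its 8 active doses (weeks 0 to 16). Both four-dose arms had their last active dose at week 12.

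**3. The two readings.**
- *One contrast averaged over the three periods:* it estimates the mean of three effects, not the PAC3 effect.
- *Three period-specific contrasts:* the PAC3 difference is reported as the protocol requires, but the PAC1 and PAC2 differences become secondary.

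Both conflict with protocol 3.1, 3.2.2 and 7.5.3.3.

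**4. Size under the averaging reading (illustration).** The documents give no effect, SD or between-period correlation for well days, so the primary endpoint's planning values stand in for them.

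The plan's own figure comes first. Inputs (protocol 7.2 and 7.5): difference 0.32, SD 0.986, two-sided 5%, 80% power.

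- n per group = 2 × (1.960 + 0.842)² × 0.986² / 0.32² = 149.1, rounded up to 150, as stated.
- At n = 150: z = 0.32 / (0.986 × √(2/150)) = 2.811, and power = Φ(2.811 − 1.960) = 80.3%.

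Now let the effect at PAC1 and PAC2 be a fraction e of the PAC3 effect, with equal variances and a common between-period correlation ρ.

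- Averaged effect as a fraction of the PAC3 effect: (1 + 2e)/3.
- SE of the average relative to PAC3 alone: √((1 + 2ρ)/3), which is 0.856 at ρ = 0.6.
- Power = Φ(2.811 × [(1 + 2e)/3] / √((1 + 2ρ)/3) − 1.960).

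| Effect at PAC1/PAC2 relative to PAC3 | Fraction of PAC3 effect estimated | Power, ρ = 0.4 | ρ = 0.6 | ρ = 0.8 |
|---|---|---|---|---|
| none (e = 0) | 1/3 | 23% | 19% | 17% |
| half (e = 0.5) | 2/3 | 68% | 59% | 52% |
| equal (e = 1) | 1 | 95% | 91% | 86% |

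The averaged contrast matches the power of PAC3 alone when (1 + 2e)/3 equals the SE factor. At ρ = 0.6 that is e = (3 × 0.856 − 1)/2 = 0.78.

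**The case against.** The strongest reply is that the SAP sentence never says the periods are averaged. It refers back to the primary model, for which SAP 15.1.3 asks for separate estimates of each arm against placebo at PAC1, PAC2 and PAC3; the only contrast written out in code there is at PAC3, and no averaged contrast is specified anywhere. On that reading the PAC3 difference is produced unchanged, the power figures above do not apply, and what remains is a label. The label alters no controlled error rate, since the step-down procedure covers only the primary analysis.

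Much of this stands. The period-specific reading is plausible, and under it the practical harm is selective emphasis among three results rather than a changed endpoint. The power figures depend on the averaging reading and on borrowed inputs; they run from 17% to 95%, so they do not establish a loss. The protocol says only that PAC1 and PAC2 may be confounded. The asthma symptom score is a secondary endpoint in the SAP but not in protocol 3.2.2, so it counts as evidence of the SAP's own convention only.

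The objection does not remove the conflict. The period-specific reading still gives secondary status to two comparisons that the protocol makes exploratory, and nothing in the SAP settles which reading applies.

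**Conclusion.** The discrepancy is real and rests on the text alone. For this endpoint the protocol names PAC3, while the SAP names all three periods, against its own practice elsewhere and without explanation.

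The effect is confined to one secondary endpoint outside formal multiplicity control. How much it matters depends on the reading. If the periods are averaged, the result estimates between one-third of the PAC3 effect and all of it as the effect at PAC1 and PAC2 goes from none to equal. Power would then lie above or below the 80% of PAC3 alone, given the borrowed planning values, equal variances and an assumed correlation of 0.4 to 0.8. If the contrasts are separate, the PAC3 estimate is intact and the error is one of status. Either way the sentence should be corrected.

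**What to change.** In SAP 15.2.1.5, replace the sentence with the two bullets used for TRSS, its components, RMS and RQLQ: the PAC3 treatment difference is the secondary analysis, and the PAC1 and PAC2 differences are exploratory. In the same edit, use the well-day label throughout, and state that the proportion of well days is how the protocol's number of days (3.2.2) and proportion of symptom-free days (7.5.3.2.4) are analysed. If using all three periods was intended, say whether they are averaged or reported separately, and record the justification before the blind is broken.

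The cost is one sentence and a label. No new modelling is needed, because the period-specific estimates required by SAP 15.1.3 already include the PAC3 contrast.

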#### 15.2.1.6. Rhinoconjunctivitis Quality of Life Questionnaire

The rhinoconjunctivitis quality of life questionnaire (RQLQ) is to be completed as a one off assessment at the end of the BAE, PAC1, PAC2 and PAC3 periods.

The RQLQ has 28 questions in the following seven domains:

- Activities
- Sleep
- Non-nose/eye symptoms
- Practical problems
- Nasal symptoms
- Eye symptoms
- Emotional
- Overall RQLQ

Document: TH005 SAP Version 2.docx  
Author: [name]

Version Number: 2.0  
Version Date: 24MAR2017

Template No: CS\_TP\_BS016 – Revision 3  
Effective Date: 01May2012

Reference: CS\_WI\_BS005

Copyright © 2012 Quintiles Transnational Corp. All rights reserved.  
The contents of this document are confidential and proprietary to Quintiles Transnational Corp. Unauthorized use, disclosure or reproduction is strictly prohibited.

---

The domains consist of the following individual questions:

- Activities: Questions 1 to 3
- Sleep: Questions 4 to 6
- Non-nose/eye symptoms: Questions 7 to 13
- Practical problems: Questions 14 to 16
- Nasal symptoms: Questions 17 to 20
- Eye symptoms: Questions 21 to 24
- Emotional: Questions 25 to 28

Refer to Appendix 3: Complete Questionnaires for the complete questionnaire. For each question subjects record how troubled they have been during the last week on a 7-point scale. For all domains, except Emotional, the scores are (0 = Not troubled to 6 = Extremely troubled). For the Emotional domain the 7-point scale is (0 = None of the Time to 6 = All of the Time).

The overall RQLQ score is the mean of all 28 responses and the individual domain scores are the means of the items within those domains.

If any individual item within a domain is missing the domain score is to be set to missing.

#### Analysis of Rhinoconjunctivitis Quality of Life Questionnaire

A point estimate and two-sided 95% confidence interval for the difference in adjusted means between the active treatment groups and placebo during the PAC1, PAC2 and PAC3 periods are to be calculated using an analysis of covariance (ANCOVA) with treatment, period and pooled region as main effects, gender, asthma status and Baseline RQLQ as covariate and a treatment by-period interaction for the Overall RQLQ score as well as each of the 7 domains individually.

- The treatment difference corresponding to the PAC3 period is to be utilised for the secondary analysis
- The treatment difference corresponding to the PAC1 and PAC2 periods are to be utilised as exploratory analyses

Observed and change from Baseline values are to be summarised by descriptive statistics for the PAC1, PAC2 and PAC3 periods by treatment group, for the Overall RQLQ score as well as each of the 7 domains individually.

#### 15.2.1.7. Mean Asthma Symptom Score

The asthma symptom scores (ASS) has six questions which are answered daily by the subject for each assessment period (BAE, PAC1, PAC2 and PAC3), describing their condition in the past 24 hours. All subjects (including non asthmatic subjects) are to describe their condition with regards to:

- Coughing

---

Document: TH005 SAP Version 2.docx  
Author: [name]

Version Number: 2.0  
Version Date: 24MAR2017

Template No: CS\_TP\_BS016 – Revision 3  
Effective Date: 01May2012

Reference: CS\_WI\_BS005

---

- Wheezing
- Shortness of breath

In addition for asthmatic subjects only, the ASS is to include the following questions:

- Limitation of activities
- Nocturnal symptoms or awakenings due to asthma
- Need for short-acting inhaled  $\beta_2$ agonist treatment

There is a 4 point scale (0 to 3) for each question. For cough, wheezing and shortness of breath symptoms the subject is to rate the severity as follows:

0 = absent

1 = Mild, barely noticeable

2 = Moderate, annoying/troublesome

3 = Severe, very annoying/ very troublesome

For limitations of activities the subject is to rate the severity as follows:

0 = Not limited

1 = Very slightly limited

2 = Slightly limited

3 = Moderately limited or worse

For nocturnal symptoms or awakenings due to asthma the subject is to rate how asthma has affected them overnight (last night) as follows:

0 = Not at all

1 = Hardly at all

2 = A few minutes disturbance

3 = Several times or more

For use of short-acting inhaled  $\beta_2$  agonist treatment the subjects are to record how many puffs of reliever medication (e.g. albuterol or salbutamol) they have used as follows:

0 = None

1 = One

2 = Two

3 = Three or more

The questions are equally weighted and the ASS for each day is to be calculated as the mean of all six questions (for asthmatic subjects) as well as the mean using only the 3 symptoms (for all subjects including asthmatics)

---

Document: TH005 SAP Version 2.docx

Author: [name]

Version Number:

2.0

Version Date:

24MAR2017

Template No: CS\_TP\_BS016 – Revision 3

Effective Date: 01May2012

Reference: CS\_WI\_BS005

Copyright © 2012 Quintiles Transnational Corp. All rights reserved.

The contents of this document are confidential and proprietary to Quintiles Transnational Corp. Unauthorized use, disclosure or reproduction is strictly prohibited.

---

separately. The ASS is therefore between 0 and 3. The mean of the daily ASS for each assessment period is to be calculated over all days with complete data.

Subjects are to be classified as asthmatic or non asthmatic based on the System Screening eCRF. Asthmatic subjects are defined as subjects with either 'Controlled' or 'Partially/Uncontrolled' asthma status and non asthmatic subjects are defined as subjects with 'No asthma'.

#### Analysis of Mean Asthma Symptom Score

The ASS is to be analysed for asthmatic subjects only, as well as all subjects (including asthmatics) separately.

A point estimate and two-sided 95% confidence interval for the difference in adjusted means between the active treatment groups and placebo is to be calculated using the same MMRM as described in Section 15.1.3 Primary Analysis of Primary Efficacy Variable.

- The treatment difference corresponding to the PAC3 period is to be utilised for the secondary analysis
- The treatment difference corresponding to the PAC1 and PAC2 periods are to be utilised as exploratory analyses

Observed and change from Baseline values are to be summarised by descriptive statistics for the PAC1, PAC2 and PAC3 periods by treatment group.

## 15.3. OTHER EXPLORATORY EFFICACY

Other exploratory efficacy analyses are to be performed for the ITT population.

### 15.3.1. OTHER EXPLORATORY EFFICACY VARIABLES & DERIVATIONS

#### 15.3.1.1. Rhinconjunctivitis Symptom Scores Measured Using Visual Analogue Scale

At start of the BAE period and the start of each PAC period subjects are to record their RSS symptoms using a Visual Analogue Scale (VAS) in their eDiaries.

Subjects are to rate their allergy symptoms on a visual scale where 0 = no allergy symptom and 10 = my allergy symptom is the worst it could possibly be with respect to the following categories:

- Runny nose
- Sneezing
- Blocked nose
- Itchy nose
- Itchy eyes
- Watery eyes
- Red eyes
- Itchy ear/palate symptoms

#### Analysis of Rhinconjunctivitis Symptom Scores Measured Using Visual Analogue Scale

Observed and change from Baseline values for each symptom's VAS score individually is to be summarised by descriptive statistics for the PAC1, PAC2 and PAC3 periods by treatment group.

#### 15.3.1.2. The Pittsburgh Sleep Quality Index

The Pittsburgh Sleep Quality Index (PSQI) assesses sleep quality during the past month and is to be completed as a once off assessment by subjects at the end of the BAE, PAC1, PAC2 and PAC3 periods. It consists of 19 self-rated questions and five completed by a bed-partner/roommate. Refer to Appendix 3: Complete Questionnaires for the complete questionnaire. For the self-rated questions there are four questions about bed and sleep times and fifteen questions (each scored in one of four categories) that elicit the quality of sleep.

The range of values for questions 5 through 10 are all 0 to 3.

Questions 1 through 9 are not allowed to be missing except as noted below. If these questions are missing then any scores calculated using missing questions are also missing. Thus it is important to make sure that all

Document: TH005 SAP Version 2.docx  
Author: [name]

Version Number: 2.0  
Version Date: 24MAR2017

Template No: CS\_TP\_BS016 – Revision 3  
Effective Date: 01May2012

Reference: CS\_WI\_BS005

questions 1 through 9 have been answered.

In the event that a range is given for an answer (e.g., '30 to 60' is written as the answer to Q2, minutes to fall asleep), split the difference and enter 45.

The total PSQI and component scores (duration of sleep, sleep disturbance, sleep latency, day dysfunction due to sleepiness, sleep efficiency, overall sleep quality and need medications to sleep) are calculated from the questionnaire and the scoring instructions in Table 2 below:

Table 2 : Scoring Instructions		
Domain	Question (Q) Result or Algorithm	Analysis Value
Duration of Sleep	Q4 > 7	0
	6 < Q4 <= 7	1
	5 <= Q4 <= 6	2
	Q4 < 5	3
Sleep Disturbance	Q5b + Q5c + Q5d + Q5e + Q5f + Q5g + Q5h + Q5i + Q5j = 0  NOTE: If Q5j-Other reason(s), is null or Q5j is null, set the value of Q5j to 0	0
	Q5b + Q5c + Q5d + Q5e + Q5f + Q5g + Q5h + Q5i + Q5j >= 1 and <= 9	1
	Q5b + Q5c + Q5d + Q5e + Q5f + Q5g + Q5h + Q5i + Q5j >= 10 and <= 18	2
	Q5b + Q5c + Q5d + Q5e + Q5f + Q5g + Q5h + Q5i + Q5j >= 19 and <= 27	3
Sleep Latency	Step 1:  If 0 <= Q2 <= 15 then set Q2 = 0  If 15 < Q2 <= 30 then set Q2 = 1  If 30 < Q2 <= 60 then set Q2 = 2  If Q2 > 60 then set Q2 = 3  Step 2:  Q5a + Q2 = 0	0
	1 <= Q5a + Q2 <= 2	1
	3 <= Q5a + Q2 <= 4	2
	5 <= Q5a + Q2 <= 6	3
Day Dysfunction Due to Sleepiness	Q8 + Q9 = 0	0
	1 <= Q8 + Q9 <= 2	1
	3 <= Q8 + Q9 <= 4	2
	5 <= Q8 + Q9 <= 6	3

Domain	Question (Q) Result or Algorithm	Analysis Value
Sleep Efficiency	Step 1:  Get difference in seconds between day and time of day Q1 and day Q3 (DIFFSEC)	
	Step 2:  Convert to hours (DIFFHOUR): Absolute value of DIFFSEC / 3600	
	Step 3:  Calculate the hours between GMT (Q1) AND GMT (Q3) (NEWTIB): If DIFFHOUR > 24 then NEWTIB = DIFFHOUR – 24 If DIFFHOUR <= 24 then NEWTIB = DIFFHOUR	
	Step 4:  Get Q4 as a percentage of NEWTIB (TMPHSE): THPHSE = (Q4 / NEWTIB) * 100	
	Step 5:  85 <= TMPHSE	0
	75 <= TMPHSE < 85	1
	65 <= TMPHSE < 75	2
	TMPHSE < 65	3
Overall Sleep Quality	Q6	Value of Q6
Need Meds to Sleep	Q7	Value of Q7
PSQI Total	Step 1:  Calculate total score (TOTAL) Duration of Sleep + Sleep Disturbance + Sleep Latency + Day Dysfunction Due to Sleepiness + Sleep Efficiency + Overall Sleep Quality + Need Meds to Sleep	TOTAL
	Step 2:  TOTAL <= 5	Good
	TOTAL > 5	Poor

